8.6 Data Summarization and Presentation

All plasma and BAL verproside and picroside II concentrations and plasma PK parameters descriptive statistics will be generated using SAS[®] Version 9.3 or higher.

Plasma and BAL concentrations of verproside and picroside II will be presented with the same level of precision as received from the bioanalytical laboratory. Summary statistics, including N, arithmetic mean, SD, CV%, median, minimum, and maximum will be calculated for all nominal concentration time points. The plasma and BAL concentrations of verproside and picroside II will be tabulated by treatment and listed by nominal sample time (Day/hour) and patient for all patients in the PK population. Patients included in the PK population but excluded from the PK per-protocol population will be included in the concentration table listings, but will be excluded from the summary statistics and noted as such in the tables. All BLQ values will be presented as “BLQ” in the concentration table listings and footnoted accordingly. For the calculation of summary statistics, BLQ concentrations will be treated as missing or 0 per defined in [Section 8.5.1](#).

The level of precision for each verproside and picroside II plasma PK parameter will be determined based on the output values, except for C parameters (i.e., C_{\max} , C_{\max_ss} , C_{\min_ss} , $C_{\text{avg_ss}}$, and C_{trough}) which will be presented with the same precision as the concentrations. For instance, t_{\max} , t_{last} , $t_{1/2}$, %Fluc, and Swing and may be presented with 2-3 decimals and AUCs, k_{el} , CL/F , V_z/F , CL_{ss}/F , and V_{z_ss}/F with 3-5 significant digits. Summary statistics, including N, arithmetic mean (mean), SD, CV%, median, minimum, maximum will be calculated for all verproside and picroside II PK parameters. In addition, geometric means (geo. mean) and geometric CV% (geo. CV%) will be presented for all C and AUC parameters. PK parameters will be tabulated by treatment and listed by patient and parameter for all patients in the PK population. Patients included in the PK population but excluded from the PK per-protocol population will be included in the PK parameter table listings, but will be excluded from the summary statistics and noted as such in the tables.

The level of precision for the summary statistics on plasma and BAL concentrations and plasma PK parameters will be the following:

- N: integer
- Minimum/Maximum: same precision as the individual values
- Mean/Median/Geo. Mean: 1 more level of precision than the individual values
- SD: 1 more level of precision than AM/median
- CV% and Geo.CV%: 1 decimal place.

Arithmetic mean and individual plasma verproside and picroside II concentrations versus time profiles on Days 1 and 54 (± 1) or Day 56 will be presented on the same plot and on linear and semi-log scales. Arithmetic mean and individual plasma verproside and picroside II C_{trough} versus time profiles will be presented on a different

plot than for Days 1 and 54 (± 1) or Day 56 and on a linear scale. Linear mean plots will be presented with and without SD and semi-log mean plots without SD.

Steady-state will be assessed by visual inspection of predose plasma C_{trough} values on Days 15 (± 2), 29 (± 2), 43 (± 2), and 54 (± 1) or Day 56 following multiple oral dose administration of YPL-001. C_{trough} values will be summarized by nominal day (i.e., 15, 29, 43, and 54), and footnotes may be included as necessary to clarify actual sampling day windows. Additional summaries and plots by actual day may be presented if deemed appropriate (e.g., significant trends observed) and requested by the Sponsor.

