3. STUDY DESIGN

This is a Phase 2a, proof-of-concept, multicenter, randomized, double-blind, double-dummy, 3-treatment, parallel study, with low and high YPL-001 doses (80 mg and 160 mg twice daily [BID]) and a placebo control, in moderate to severe COPD male and female patients.

Sixty (60) patients will be enrolled and randomized into 3 treatment groups (20 patients per group). Patients will participate only once. An approximately equal number of current and ex-smokers will be enrolled in the study.

Screening of patients will occur within 14 days of Day 1 (inclusive) of the Run-in Period.

Following screening, eligible patients will discontinue non-permitted respiratory drugs and enter a 14 ± 2 days Run-in Period during which patients will be given albuterol taken on an as required basis and daily tiotropium 18 μ g to be administered at home. They will record their daily symptoms in an electronic diary (e-diary) throughout the Run-in Period.

Patients will return to the clinical research unit (CRU) in the morning of Day -3 to -1 for Check-in of the Treatment Period to confirm their eligibility and undergo Check-in scheduled study procedures. Patients will return to the CRU on the morning of Day 1 to be randomized and receive one of the 3 treatments and undergo all scheduled study procedures. Patients will return on the morning of Days 15 (± 2 days), 29 (± 2 days), 43 (± 2 days), 54 (± 1 day), and 56 of the Treatment Period for study drug administration and procedures. Prior to each release from the CRU, patients will receive sufficient doses to be self-administered at home until the next morning visit at the CRU. Patients will continue recording their daily symptoms via the e-diary throughout the Treatment Period.

YLP-001 and placebo will be administered approximately every 12 hours under fasting conditions.

Patients will remain ambulatory or seated upright for 1 hour following each study medication administration.

Safety and tolerability will be assessed throughout the study through physical examinations, vital signs, pulse oximetry, electrocardiograms (ECGs), clinical laboratory tests, and adverse events (AEs).

Assessment of respiratory symptoms and symptom burden in YPL-001 and placebo treatments will be performed daily through patient self-report of PEF, major and minor symptoms of COPD exacerbation, dyspnea, and activity.

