$t_{1/2}$	$t_{1/2}$	Apparent first-order elimination half-life.	Calculated as: $\ln(2)/k_{el}$
CL/F	CL/F	Apparent total plasma clearance after extravascular administration (verproside only).	Calculated as: $Dose/AUC_{0-\infty}$
V_z/F	V_z/F	Apparent volume of distribution during the terminal elimination phase after extravascular administration (verproside only).	Calculated as: $Dose/(k_{el} \times AUC_{0-\infty})$

Following Multiple Doses of YLP-001 - Day 54 (\pm 1) or Day 56			
Parameter	Label to be Used in Tables	Definition	Method of Determination
AUC _τ	AUCtau	AUC over the final 12-hour dosing interval (τ) at steady state (e.g., 0-12 hours).	Calculated using the Linear Trapezoidal with Linear Interpolation Method. May be extrapolated using the k_{el} , if C_t occurs prior to 12 hours postdose.
AUC _{0-t}	AUC0-t	AUC from time zero to time t , where t is the time of the C_t .	Calculated using the Linear Trapezoidal with Linear Interpolation Method.
C _{max_ss}	Cmax_ss	Maximum observed plasma concentration during a dosing interval at steady state.	Taken directly from bioanalytical data.
C _{min_ss}	Cmin,ss	Minimum observed/measured non-zero concentration during a dosing interval at steady state.	Taken directly from bioanalytical data.
t _{max_ss}	tmax_ss	Time to reach C _{max_ss} (obtained without interpolation).	Observed
C _{trough}	Ctrough	Plasma concentration observed at the end of a dosing interval at steady state. Presented as predose in the morning Days 15 (\pm 2), 29 (\pm 2), 43 (\pm 2), and 54 (\pm 2) (following PM dosing on Days 14 (\pm 2), 28 (\pm 2), 42 (\pm 2), and 54 (\pm 1) or 56, respectively).	Taken directly from bioanalytical data.
C _{avg_ss}	Cavg_ss	Average plasma concentration at steady state.	Calculated as: AUC_{τ}/τ
%Fluc	%Fluc	Percent peak-to-trough fluctuation at steady-state.	Calculated as: $(C_{max_ss} - C_{min_ss})/C_{avg_ss} \times 100$
Swing	Swing	Percent swing at steady-state.	Calculated as: $(C_{max_ss} - C_{min_ss})/C_{min_ss} \times 100$

Following Multiple Doses of YLP-001 - Day 54 (\pm 1) or Day 56			
Parameter	Label to be Used in Tables	Definition	Method of Determination

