k_{el}	kel	Apparent first-order terminal elimination rate constant, which represents the fraction of drug eliminated per unit time.	Calculated from a semi-log plot of the plasma concentration versus time curve, calculated by linear least-squares regression analysis using the maximum number of points in the terminal log linear phase (e.g., three or more non-zero plasma concentrations).
$t_{1/2}$	$t_{1/2}$	Apparent first-order elimination half-life.	Calculated as: $\ln(2)/k_{el}$
CL_{ss}/F	CL_{ss}/F	Total body clearance estimated at steady-state after oral administration (verproside only).	Calculated as: $Dose/AUC_{\tau}$
$R_{A,AUC}$	RA,AUC	Accumulation ratio	Calculated as: AUC_{τ} / AUC_{0-12} (on Day 1) If AUC_{0-12} on Day 1 or AUC_{τ} on Day 54 (\pm 1) or 56 cannot be calculated for a patient, then no $R_{A,AUC}$ value will be presented for that patient.
$V_{z,ss}/F$	$Vz,ss/F$	Apparent volume of distribution at steady state.	Calculated as: $(CL_{ss}/F)/k_{el}$

For the calculation of the PK parameters that depended on the dose (CL/F , V_z/F , CL_{ss}/F , and $V_{z,ss}/F$) verproside content is 28.96 and 57.92 mg for the 80 and 160 mg YPL-001 dose levels, respectively.

Actual sample times will be used in the calculations. Patients for whom there are insufficient data to calculate the PK parameters (at least 3 consecutive measurable concentrations) will be included in the concentration tables only and excluded from the pharmacokinetic and statistical analyses.

For the calculation of the PK parameters, plasma concentrations below the limit of quantitation (BLQ) prior to the first quantifiable concentration will be set to 0.00 and plasma concentrations BLQ after the first quantifiable concentration will be treated as missing.

Plasma verproside and picroside II C_{trough} concentrations will be presented. Although C_{trough} concentrations are related to the PM dose given on Days 14 (\pm 2), 28 (\pm 2), 42 (\pm 2), and 53 (\pm 2), they will be labeled and referred with in the TFLs as AM predose time point on Days 15 (\pm 2), 29 (\pm 2), 43 (\pm 2), and 54 (\pm 1) or Day 56.

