Table 11-11 Summary of Plasma Verproside Pharmacokinetic Parameters Following Single Oral YPL-001 Doses of 80 mg and 160 mg in COPD Patients – Day 1

Verproside Pharmacokinetic Parameters	Treatment A YPL-001 80 mg	Treatment B YPL-001 160 mg
AUC ₀₋₁₂ (pg*hr/mL) ^a	XXX (XXX) (N=X)	XXX (XXX) (N=X)
AUC _{0-t} (pg*hr/mL) ^a	XXX (XXX) (N=X)	XXX (XXX) (N=X)
AUC _{0-inf} (pg*hr/mL) ^a	XXX (XXX) (N=X)	XXX (XXX) (N=X)
C _{max} (pg/mL) ^a	XX (XX) (N=X)	XXX (XXX) (N=X)
t _{max} (hr) ^b	XXX (XXX, XXX) (N=X)	XXX (XXX, XXX) (N=X)
t _{last} (hr) ^b	XXX (XXX, XXX) (N=X)	XXX (XXX, XXX) (N=X)
k _{el} (1/hr) ^c	XXX± XXX (N=X)	XXX± XXX (N=X)
t _{1/2} (hr) ^c	XXX± XXX (N=X)	XXX± XXX (N=X)
CL/F (L/hr) ^c	XXX± XXX (N=X)	XXX± XXX (N=X)
V _z /F (L) ^c	XXX± XXX (N=X)	XXX± XXX (N=X)
R _{A,AUC} ^c	XXX± XXX (N=X)	XXX± XXX (N=X)

^a: Presented as geo. mean (geo. CV%)

^b: Presented as median (minimum, maximum)

^c: Presented as arithmetic mean ± SD

Treatment A: Multiple oral doses of YPL-001 80 mg BID on Days 1 – 55

Treatment B: Multiple oral doses of YPL-001 160 mg BID on Days 1 – 55

Note: Patients following up to Amendment version 5 of the protocol also received a morning dose on Day 56.

Source: Tables 14.2.4.1.3 and 14.2.4.1.5

Note to Programmer: For verproside and picroside II tables on Day 54 (± 1) or 56 the PK parameters will be: AUC_τ, AUC_{0-t}, C_{max_ss}, t_{max_ss}, C_{min_ss}, t_{last}, C_{trough}, C_{avg_ss}, %Fluc, Swing, k_{el}, t_{1/2}, CL_{ss}/F, V_{z_ss}/F, and R_{A,AUC}. Note that in-text Table 11-17 will be in a similar format as for Table 11-13:

Table 11-13 Statistical Comparisons of Dose-Normalized Plasma Verposide Pharmacokinetic Parameters Following Multiple Oral YPL-001 Doses of 160 mg Versus Multiple Oral YPL-001 Doses of 80 mg and in COPD Patients – Day 54 (\pm 1) or Day 56 (Treatment B Versus Treatment A)

Verposide Pharmacokinetic Parameter	Geometric LSM		Geometric Mean Ratio (%)	90% Confidence Intervals
	Treatment B (test, N=X)	Treatment A (reference, N=X)		
AUC _τ (pg*hr/mL)	XX	XX	XX	XX – XX
AUC _{0-τ} (pg*hr/mL)	XX	XX	XX	XX – XX
C _{max_ss} (pg/mL)	XX	XX	XX	XX – XX

Parameters were dose-normalized (to 80 mg YLP-001) and ln-transformed prior to analysis.
 Geometric least square means (LSMs) were calculated by exponentiating the LSM from the ANOVA.
 % Geometric Mean Ratio = $100 \times (\text{test}/\text{reference})$
 Treatment A: Multiple oral doses of YPL-001 80 mg BID on Days 1 – 55

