Table 14.2.4.1.1 Plasma Verproside Concentrations (pg/mL) Following Single and Multiple Oral YPL-001 Doses of 80 mg in COPD Patients - Days 1 to 54 (+/- 1) or Day 56 (Treatment A)

Subject Number	Sample Times (Day / hr)											
	Day X				- Day X --				Day XX	Day XX	Day XX--	
XX	XX	XX	XX	XX	XX	XX	XX	Predose	Predose	XX	XX	XX
XXXX	BLQ	XX	XX	XX	XX	XX	XX	BLQ	XX	XX	XX	XX
XXXX	BLQ	XX	XX	XX	XX	XX	XX	XX	XX	XX	XX	XX
XXXX	XX	XX	XX	XX	XX	XX	XX	XX	XX	XX	XX	XX
N	XX	XX	XX	XX	XX	XX	XX	XX	XX	XX	XX	XX
Mean	XX	XX	XX	XX	XX	XX	XX	XX	XX	XX	XX	XX
SD	XX	XX	XX	XX	XX	XX	XX	XX	XX	XX	XX	XX
CV%	XX	XX	XX	XX	XX	XX	XX	XX	XX	XX	XX	XX
Median	XX	XX	XX	XX	XX	XX	XX	XX	XX	XX	XX	XX
Maximum	XX	XX	XX	XX	XX	XX	XX	XX	XX	XX	XX	XX
Minimum	XX	XX	XX	XX	XX	XX	XX	XX	XX	XX	XX	XX

Footnotes to include, as appropriate:

For the calculation of summary statistics and pharmacokinetic parameters, values on Days 1 and 54+/-2 that are below the lower limit of quantitation (BLQ) of 50.0 pg/mL are treated as 0.00 before the first quantifiable concentration on each study day and as missing elsewhere. In addition, predose BLQ values on Days 15+/-2 to 56 were set to 0.00.

. = Value missing or not reportable

Programmer Note:

PK Time points are listed in Sections 8.1.1 and 8.1.2 of this SAP.

Please see text in Section 8.6 for description of significant figures/decimals to be used for descriptive statistics.

Program : /AAXXXX/ECR/sas_prg/pksas/PROGRAMNAME.sas DDMMYYYY HH:MM

Note: Tables 14.2.4.1.3 - 6 (verproside) and 14.2.4.2.3 - 6 (picroside II) will be in a similar format:

Page X of X

Table 14.2.4.1.3 Plasma Verproside Pharmacokinetic Parameters Following a Single Oral YPL-001 Dose of 80 mg in COPD Patients - Day 1
 (Treatment A)

Subject Number	Parameters								
	Param (units)								
XX	XXX								
XX	XXX								
XX	XXX								
N	XXXX								
Mean	XXXX								
SD	XXXX								
CV%	XXXX								
Median	XXXX								
Minimum	XXXX								
Maximum	XXXX								
Geom. Mean	XXXX	NC	XXXX	NC	NC	XXXX	NC	NC	NC
Geo. CV%	XXXX	NC	XXXX	NC	NC	XXXX	NC	NC	NC

NC = Not calculated.

. = Value missing or not reportable.

Programmers note:

Geo. Mean and Geo. CV% will be calculated for C and AUC parameters only.

Please refer to Section 8.5.1 for list of pharmacokinetic parameters on each study day. Significant figures/decimals to be used for PK parameters will be specified by the PKist upon review of the data. Please refer to Section 8.6 for description of significant figures/decimals to be used for descriptive statistics.

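### The accumulation ratio R_A,AUC is summarised by an arithmetic mean of patient ratios, which is biased upward; a geometric mean with a 90% CI would match how the plan treats AUC elsewhere (minor)

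*SAP*

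**What the plan says.** SAP Section 8.5.1 (Table 2) defines R_A,AUC for each patient as AUC_tau on Day 54 (±1) or 56 divided by Day 1 AUC_0-12. If either AUC cannot be calculated, no ratio "value will be presented for that patient". AUC_tau is the "AUC over the final 12-hour dosing interval" at steady state.

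Three places fix how the ratio is summarised:

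- Section 8.6, for every parameter: "Summary statistics, including N, arithmetic mean (mean), SD, CV%, median, minimum, maximum will be calculated for all verproside and picroside II PK parameters". It then adds: "In addition, geometric means (geo. mean) and geometric CV% (geo. CV%) will be presented for all C and AUC parameters".
- Section 12.1, Table 11-11 shell: the R_A,AUC row carries footnote c, "Presented as arithmetic mean ± SD". The AUC rows of the same table carry footnote a, geometric mean with geometric CV%. Tables 11-12, 11-15 and 11-16 follow the same format.
- Section 12.2, programmers' note to the Table 14.2.4.1.3 shell: "Geo. Mean and Geo. CV% will be calculated for C and AUC parameters only".

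For the plan's other AUC ratio, 160 mg against 80 mg, Section 8.7 specifies a geometric mean ratio with 90% CI. The shells for Tables 11-13 and 14.2.4.1.8 state that the parameters are ln-transformed first. The remaining check on time-dependence is graphical: "Steady-state will be assessed by visual inspection of predose plasma" troughs.

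**The concern.** The plan treats AUC as a log-scale quantity when it summarises AUC and when it compares doses, but leaves the log scale when it divides one AUC by another within a patient. The arithmetic mean of positive ratios lies above their geometric mean in every data set where the ratios differ. Where the same patients contribute to both days, the geometric mean of the ratios equals the quotient of the two geometric mean AUCs. The report would then print an R_A,AUC larger than the quotient a reader obtains from its own AUC rows.

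The summary also depends on which day is the numerator. With no accumulation, the mean of Day 54/56 over Day 1 and the mean of Day 1 over Day 54/56 both have an expectation above 1.

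What is at stake is the accuracy of one descriptive estimate under an exploratory objective. The error runs in a known direction, and no interval is planned to show whether 1 is compatible with the data.

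**Working it through.** The SAP states no variability, half-life or accumulation figure for this point, so there is no planned number to reproduce.

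**Inputs.** From the SAP: 20 patients per group (Section 3), a 12-hour dosing interval (Section 8.5.1), and the summary rules above. Assumed: within-patient CV of AUC from 20 to 50%, and half-life from 1 to 4 h. Section 8.5.1 says only that the half-life reported in an earlier study means troughs below the quantitation limit may occur; it gives no value.

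**Step 1: expectation with no accumulation.** Let a patient's two AUCs be log-normal with the same median and independent within-patient errors, with ln-scale variance s² = ln(1 + CV²). The patient's own level cancels, so ln(ratio) ~ N(0, 2s²). Then

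- geometric mean and median of the ratio = exp(0) = 1;
- arithmetic mean = exp(2s²/2) = exp(s²) = 1 + CV²;
- SD of the ratio = (1 + CV²) × √((1 + CV²)² − 1).

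At CV 30%: mean = 1 + 0.09 = 1.09; SD = 1.09 × √(1.1881 − 1) = 0.47.

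**Step 2: results at n = 20.** Simulation with 100,000 replicates, true ratio 1. SE is SD/√20.

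| Within-patient CV (assumed) | Expected arithmetic mean | SD | SE | Bias/SE | Trials with mean > 1 | Expected sample median |
|---|---|---|---|---|---|---|
| 20% | 1.04 | 0.30 | 0.066 | 0.6 | 72% | 1.003 |
| 30% | 1.09 | 0.47 | 0.106 | 0.9 | 80% | 1.008 |
| 40% | 1.16 | 0.68 | 0.152 | 1.0 | 86% | 1.012 |
| 50% | 1.25 | 0.94 | 0.210 | 1.2 | 90% | 1.017 |

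An unbiased summary would fall above 1 in about half of trials. The geometric mean has a median of 1.00 over simulated trials at every CV shown. The arithmetic mean reaches an expected 1.20 only at CV = √0.20 ≈ 45%.

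**Step 3: size of true accumulation, for scale.** With linear one-compartment kinetics, R = 1/(1 − 2^(−12/t½)). This gives 1.0002, 1.016, 1.067 and 1.14 at half-lives of 1, 2, 3 and 4 h. At 1 to 2 h, the bias at CV 20% or more (0.04 upward) is larger than the true excess over 1 (0.016 or less). At 3 h and CV 20% it is smaller: about 0.04 against 0.067. At 4 h the true excess of 0.14 also outweighs the 0.09 bias at CV 30%.

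**The case against.** The strongest reply is that nothing depends on this row. The SAP attaches no test, threshold, interval or decision to R_A,AUC. Section 8.6 already requires the median, minimum and maximum for every PK parameter, so the post-text tables carry a summary that is off by less than 2% up to CV 50%. Geometric means of AUC are tabulated for both days, individual values are listed, and Day 1 and Day 54/56 profiles share a plot. The SD and N printed beside the mean show how imprecise it is. The notes heading Sections 12.1 and 12.2 let table content change, so a geometric mean could be added anyway. All of this stands, and it limits the severity.

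It does not remove the flaw. The in-text row shows only the biased statistic. The quotient of the two tabulated geometric means is a paired estimate only when the same patients contribute to both days, and Section 8.5.1 allows AUC_tau or R_A,AUC to be not calculable for some patients.

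A reader might go further and infer that the trial would report accumulation of a drug that does not accumulate. The documents do not support that. The mean exceeds 1 in expectation, not always: at CV 20% and 30%, 28% and 20% of simulated trials give a mean of 1 or less. The SAP states neither CV nor half-life, so neither the absence of accumulation nor a large bias is established. Nor does the bias always exceed the quantity measured, as the 3 h and 4 h cases show.

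**Conclusion.** The point holds as a minor one. The plan summarises a within-patient AUC ratio on the arithmetic scale, against its own geometric treatment of AUC and of the dose ratio. With no accumulation, the expected in-text figure is 1 + CV²: 1.04 to 1.25 for within-patient CV of 20 to 50%. The bias is small at CV 20% or below, at most 0.09 up to CV 30%, and reaches 0.20 only near CV 45%.

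The sizes rest on log-normal AUCs, independent errors on the two days and an assumed CV. The direction does not: the arithmetic mean exceeds the geometric mean whenever the patient ratios differ. The in-text figure may overstate accumulation and disagree with the quotient of the geometric mean AUCs. No formal conclusion changes, and the post-text median remains a nearly unbiased check.

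**What to change.** In Section 8.6, name R_A,AUC alongside the C and AUC parameters for geometric summary, and add a 90% CI. For each patient take d = ln(AUC_tau) − ln(Day 1 AUC_0-12). Report exp(mean d) as the geometric mean, 100 × √(exp(s_d²) − 1) as the geometric CV%, and exp(mean d ± t(0.95, n−1) × s_d/√n) as the 90% CI.

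In the shells for Tables 11-11, 11-12, 11-15 and 11-16, replace footnote c on the R_A,AUC row accordingly. In the post-text PK parameter shells, amend the programmers' note that limits geometric statistics to C and AUC parameters. Keep the median and range already planned. While editing the row, clarify why it appears in Table 11-11, a Day 1 table, when the ratio needs Day 54/56 data.

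Leave CL/F and CLss/F as they are; an arithmetic mean is a legitimate summary of clearance, and no error is shown there.

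The cost is a few words in the SAP and shells and minimal code. No new data are needed.

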For the calculation of summary statistics and PK parameters, BLQ plasma concentrations will generally be set to 0 prior to the first quantifiable concentration on each study day and to missing thereafter. Based on the reported mean $t_{1/2}$ of plasma verproside and picroside II following the BID administration of 80 mg YPL-001 in a previous multiple ascending dose (MAD) study in healthy subjects, C_{trough} that are BLQ may be expected in this study. Therefore, C_{trough} BLQ concentrations measured at predose on Days 15 (± 2), 29 (± 2), 43 (± 2), and 54 (± 1) or Day 56 will be set to 0 for the calculations of summary statistics and PK parameters.

The k_{el} will be determined using linear regressions composed of least 3 data points. The k_{el} will not be assigned if 1) the terminal elimination phase is not apparent, 2) if t_{max} is one of the 3 last data points, or 3) if the R^2 value is less than 0.8. For the analysis on Day 1, the k_{el} will only be reported if the $t_{1/2}$ of verproside or picroside II can be appropriately estimated from a 12-hour sampling period following dosing. In cases where the k_{el} interval is not assigned, the values of AUC_{0-inf} , $t_{1/2}$, CL/F , V_z/F , AUC_τ , CL_{ss}/F , V_{z_ss}/F , and $R_{A,AUC}$, as applicable, are considered not calculable and will not be reported. Wherever the resulting $t_{1/2}$ is more than half as long as the sampling interval, the k_{el} values and associated parameters (AUC_{0-inf} , $t_{1/2}$, CL/F , V_z/F , AUC_τ , CL_{ss}/F , V_{z_ss}/F , and $R_{A,AUC}$ as applicable) may not be presented as judged appropriate and in accordance with Celerion SOPs.

All available data will be included in the concentration and PK parameter tables to the extent possible. Patients will be excluded from the PK population if they significantly violate a protocol inclusion or exclusion criteria, deviate significantly from the protocol, or if data are unavailable or incomplete, which may influence the PK analysis.

Except if otherwise specified, available concentration and PK data of each patient will be included in the summary statistics and statistical comparisons for PK parameters.

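### Trough values below the quantitation limit are set to 0, yet the SAP orders a geometric mean and geometric CV% for Ctrough, which zeros make 0 or undefined

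*SAP*

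**What the plan says.** **The zero rule.** Section 8.5.1 draws on the half-life seen in an earlier multiple-dose study and anticipates troughs "that are BLQ may be expected in this study". It therefore directs that BLQ troughs on Days 15, 29, 43 and 54 (or 56) "will be set to 0 for the calculations of summary statistics and PK parameters". The footnote to the concentration table shell in Section 12.2 repeats this: "In addition, predose BLQ values on Days 15+/-2 to 56 were set to 0.00".

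**The geometric statistics.** Section 8.6 names the C parameters as Cmax, Cmax_ss, Cmin_ss, Cavg_ss "and C_{trough}) which will be presented with the same precision as the concentrations". It then orders that "geometric means (geo. mean) and geometric CV% (geo. CV%) will be presented for all C and AUC parameters". The programmer note to the post-text parameter shell in Section 12.2 says the same: "Geo. Mean and Geo. CV% will be calculated for C and AUC parameters only".

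**Where they meet.** The note under Table 11-11 in Section 12.1 begins "For verproside and picroside II tables on Day 54 (± 1) or 56 the PK parameters will be", and its list includes Ctrough. Those tables follow the Table 11-11 format, in which AUC and Cmax are shown as geometric mean (geometric CV%).

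**What links the two.** On BLQ values, Section 8.6 says only that "BLQ concentrations will be treated as missing or 0 per defined in" Section 8.5.1, which leads back to the zero rule. Nothing exempts Ctrough or says how a zero enters a log-scale statistic.

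**The concern.** Both instructions are in force, and they cannot both be carried out sensibly once an arm has one BLQ trough. The SAP foresees that case, so this is a stated rule that fails in an expected situation, not a missing detail.

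The programmer would have to improvise. One outcome is a geometric mean of 0 or an empty cell. The other is a geometric mean of the quantifiable patients only, printed beside an arithmetic mean and an N that include the zeros. That second figure can never fall below 50 pg/mL. A reader of the in-text table would take it as the typical trough of the whole arm.

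**Working it through.** The SAP states no figure on this point, so there is none to reproduce. The check works from the definitions.

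**Inputs from the SAP**
- LLOQ 50.0 pg/mL (Section 8.2)
- 20 patients per arm (Section 3)
- BLQ trough = 0 (Section 8.5.1)
- Geometric mean and geometric CV% for every C parameter (Section 8.6)

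**Assumed, because the SAP is silent:** BLQ share, between-patient CV, lognormal troughs, independent patients.

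**Step 1: what a zero does.** Geometric mean = exp(mean of ln x). Geometric CV% = 100 × sqrt(exp(var of ln x) − 1). An illustrative arm of 20 with 6 zeros and 14 positive values gives:
- mean of ln x = −infinity, so the geometric mean is 0 (undefined if ln 0 is not accepted)
- SD of ln x is not a number, so the geometric CV% is undefined
- with the zeros dropped: geometric mean 95.1 pg/mL and geometric CV 25.4%, on N = 14 instead of 20

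**Step 2: how easily it happens.** P(at least one BLQ in 20) = 1 − (1 − p)^20:

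| Assumed BLQ rate p | Probability |
|---|---|
| 1% | 18% |
| 5% | 64% |
| 10% | 88% |
| 25% | 99.7% |

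**Step 3: bias if zeros are dropped.** For lognormal troughs with a share p below the LLOQ, let σ = sqrt(ln(1 + CV²)), z = Φ⁻¹(p) and λ = φ(z)/(1 − p). The geometric mean of the quantifiable patients exceeds the true one by the factor exp(σλ). For CV 50%, 80% and 120%, σ = 0.472, 0.703 and 0.944.

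| BLQ share | λ | CV 50% | CV 80% | CV 120% |
|---|---|---|---|---|
| 10% | 0.195 | 1.10 | 1.15 | 1.20 |
| 25% | 0.424 | 1.22 | 1.35 | 1.49 |
| 50% | 0.798 | 1.46 | 1.75 | 2.12 |

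Worked case, 25% BLQ and CV 80%: the true geometric mean is 50 × exp(0.703 × 0.674) = 80.4 pg/mL. The reported value is 80.4 × exp(0.703 × 0.424) = 108.2 pg/mL, on about 15 of 20 patients.

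**Step 4: which outputs are touched.**
- Ctrough appears in the Day 54 (±1)/56 parameter lists, not in the Day 1 lists.
- Cmin_ss is defined in Table 2 on non-zero concentrations and escapes the problem.
- The concentration table shell carries no geometric statistics.
- Section 8.7 analyses AUCτ, AUC0-t and Cmax_ss only.
- Section 8.6 plots troughs as arithmetic means and individual values on a linear scale, where zeros are admissible.

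**The case against.** The strongest reply is that little depends on these cells. They are descriptive and belong to an exploratory endpoint. Section 8.6 also requires N, arithmetic mean, SD, CV%, median, minimum and maximum, and BLQ values are printed as such in the concentration tables. A minimum of 0 beside a geometric mean above 50 would be visible in the post-text table. The parameter shell already has a code for values not calculated, and Sections 12.1 and 12.2 allow table content to change with the data. An uncomputable cell could therefore be reported without harm. Only the dropping of zeros biases anything, and the SAP does not say that zeros will be dropped.

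Most of this stands, and it limits the point to a contained correction. It does not remove the conflict. The not-calculated code is not tied to any rule for Ctrough. Leaving the content open to change defers a foreseeable choice until the BLQ pattern is known. The in-text tables are more exposed than the post-text ones, because their format for C and AUC parameters shows only the geometric mean, geometric CV% and N.

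**Conclusion.** The point holds as a conflict between Sections 8.5.1 and 8.6, repeated in the shells. With any BLQ trough, the ordered geometric mean is 0 or undefined and the geometric CV% is undefined. If zeros are dropped, the trough is overstated by the factors in the table above. The size rests on assumed CVs and BLQ shares and on lognormal troughs. The upward direction follows from removing the lowest values.

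The effect is confined to descriptive Ctrough cells in the Day 54 (±1)/56 parameter tables and any by-day Ctrough parameter summary. A reader might infer more, but the SAP does not support it:

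- *That the steady-state assessment is compromised.* Section 8.6 makes it by visual inspection of trough values, and the planned plots do not use geometric means.
- *That the dose comparison is distorted.* Fewer quantifiable 80 mg patients would narrow an apparent dose difference in trough geometric means, but no planned analysis compares them.
- *That the bias could be several-fold.* At 75% BLQ the same formula gives 1.82-3.32, but only about 5 of 20 patients would remain. Nearer to 100% BLQ there is hardly a statistic left to describe. The SAP gives no reason to assume such rates.

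**What to change.** In Section 8.6, and in the notes to the Day 54 (±1)/56 parameter tables, state one rule: for any dose and day with at least one BLQ trough, the geometric mean and geometric CV% of Ctrough are shown as NC. In their place, report n (%) BLQ with median, minimum and maximum, counting BLQ as 0.

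The tables concerned are 11-12 and 11-16 in the text, and 14.2.4.1.4, 14.2.4.1.6, 14.2.4.2.4 and 14.2.4.2.6 after the text. The Day 1 tables carry no Ctrough and need no change.

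The cost is one sentence, the table notes and one added row. The geometric mean is not shown in the affected cells, where it could not be validly calculated under the zero rule.
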